	An emergence of resistances for both insecticide and antimalarial drugs like ACTs has been reported in several African countries. In addition, the currently implemented strategies are restricted to indoor controls and populations remain exposed to Plasmodium transmission during their outdoor activities. The strategies also fail to target asymptomatic Plasmodium carriers who constitutes, most of the infected people in endemic regions and perpetuate the disease transmission over time. Hence, the need to accurately identify and treat asymptomatic infectious human reservoirs. Recent investigations that Artemisia afra tea infusions can effectively treat malaria in endemic communities, with gametocidal effects and no reported toxicity suggest its probable usefulness in the elimination of plasmodium reservoirs in endemic settings. However, no clinical trials have not been conducted to ascertain the activity level and optimal dosage of Artemisia afra tea in the treatment of asymptomatic reservoirs.
Hypothesis	An optimal dosage of artemisia afra tea infusions is effective, safe, and well tolerated in eliminating plasmodium reservoirs.
General objective	To find the activity level and accepted optimal dose concentration, dose frequency, length of treatment, and formulation (flavor) of A.afra in treating Plasmodium reservoirs.
Specific objectives	To assess participants' response (treatment efficacy) to varying dose concentrations, dose frequency, length of treatment, and formulation of Artemisia afra treatment. To identify the content of the content o
	• To identify the most acceptable dose concentration, dose frequency, length of treatment, and formulation (flavor) of Artemisia treatment.
	• To assess the safety (adverse side effects) of Artemisia afra treatment in participants by dose concentration, dose frequency, length of treatment, and formulation. As a commonly used tea, no toxicity is expected.
	To assess variability of plasmodium test predictive values between mRDT, rtPCR, and direct blood smear observation in asymptomatic persons.
Outcomes	 Major outcome Decrease in parasite load over time Secondary outcomes
	Decrease in gametocyte load in carriers with Artemisia afra tea by dose concentration, dose frequency, length of treatment, and formulation.

- Acceptability (adherence and completion) of Artemisia afra treatment by dose concentration, dose frequency, length of treatment, and formulation (flavor).
- Safety (ASEs) of *Artemisia afra* treatment in participants by dose concentration, dose frequency length of treatment, and treatment formulation.
- Likelihood and variability in the rate of reservoir elimination with treatment, compliance/ acceptability, and occurrence of side effects /adverse events in different treatment arms.

Study design and methods

Design: The study is a Phase 2 randomized controlled, partial-blind, parallel group study in plasmodium infected *asymptomatic* adults 18 years and older, with 8 study arms. It will use the adapted Zelen design, which has two steps in the consent process. In the first step, there is an informed consent from all participants for a cohort lifestyle study. According to this consent, participants are randomized without knowledge about the detailed protocol.

In the second step, only participants from the intervention group will receive the information about the intervention and the second consent will be obtained from them. The participants who will decline to participate to an intervention will continue in the cohort study, as the control group. Duration of study: The study duration is 35 days (5 weeks) for each participant.

Treatment groups (TG):

- **TG 1**: Group of 8 persons receiving *A. afra* infusions of 5g/1liter of water, 3drinks a day, daily for 1week (7 days) (current recommendation).
- TG 2: Group of 8 persons receiving A. afra infusions of 5g/500ml of water, 2drinks a day, daily for 1week (7 days) (increase concentration and decrease dose frequency).
- **TG 3:** Group of 8 persons receiving *A. afra* infusions,5g/1liter of water, 3drinkss a day, weekly for 4weeks (decrease dose frequency and increase length of treatment).
- TG 4: Group of 8 persons receiving flavored *A. afra* infusions, 5g/1liter of water, 3drinks a day, daily for1week (7 days) (current treatment with improved taste).
- **TG 5:** Group of 8 persons flavored *A. afra* infusions, 5g/500ml of water, 2drinks a day, daily for 1 week (7 days) (improved taste, increase concentration and decrease dose frequency).
- TG 6: Group of 8 persons receiving flavored A. afra infusions, 5g/1liter of water, 3drinks a day, weekly for 4weeks (improved taste, decrease dose frequency and increase length of treatment);
- TG 7: Group of 4 persons receiving flavored placebo infusions, 5g/liter of water, 3drinks a day,
 daily for 1week (7 days) (improved taste with no active molecule);
- **TG 8**: Group of 4 participants receiving regular tea placebo taken as desired, daily for 1 week (7 days) (Regular tea with no active molecule).

Randomization. The randomization method will be a permuted block randomization, with a block size of either 14 or 28 at random, and with a two-to-one allocation ratio for each active arm against two different control arms (2:2:2:2:2:1:1)

Blinding: Partial blind.

Data collection: Data will be captured through an observation worksheet and entered in Electronic Case Reporting Forms (eCRF).

Figure 2 and 3 show study design

[figure not shown]

Figure 2. Screening and recruitment of study participants.

[figure not shown]

Figure 3. Algorithm to find the activity level, optimal dosage, and accepted formulation of *Artemisia afra* in eliminating plasmodium reservoirs.

Blood sample schedule: Five blood samples (approximately 1mL each) will be collected at Visit 1 (Day 0), Visit 2 (Day 7), Visit 3 (Day 14), Visit 4 (day 28), and visit 5 (day 35).

Study visits/assessment schedules: Five visits at Day0, Day7, Day14, Day28 and Day35.

Clinical symptoms (mild malaria symptoms): Clinical symptoms that may occur during the trial period will be assessed daily by site (observing) staff and recorded in the home or site visit worksheets throughout the study period.

Adverse side effects (ASEs) and adverse events (AEs): ASEs are not expected. Participants will be assessed daily by site staff during site and home visits/calls, within the 35 days study period and any AEs will be recorded in the eCRF (case report form).

ASEs and AEs leading to withdrawal will also be collected throughout the study period, by interviewing participants during site and home visits, and by reviewing of available medical records.

Written informed consent will be obtained before conducting any study related procedures or treatment on the participants. Participants will first be informed about the aim of the study,

designs, potential gain, and their right to stop at any moment if they accept to enter the study. Then they will be requested to sign a written informed consent. Number of study Fifty-six positive participants have to be enrolled per site, making 112 participants in the whole participants: study. To reach the required number of gametocyte carriers, 635 persons will be RDT tested in Buea (Southwest region) where the expected positive RDT was 9.8.% in Demographic health survey (DHS) 2018 and drop-out rate was set at 10%. In Huye (South region), the expected positive RDT was 14.4% in Malaria indicator survey (MIS)2017 and drop-out rate was set at 10%, hence 432 persons will be RDT tested to reach the required number of gametocyte carriers. Study All students and staff members of the University will be invited to participate in the study. population Participants will be included in the study if in good health (based on physical examination and /Participants medical history), and if they meet all specified eligibility criteria. characteristics/ Inclusion criteria for trial allocation groups Study sites/ Asymptomatic Plasmodium positive students or workers from the selected study universities, aged 18 years and above who provide written informed consent. **Exclusion criteria for trial allocation groups** 1. To have a known hypersensitivity to any ingredients of the tea. 2. Currently taking any malaria drug for prevention or treatment. 3. To have participated in another malaria drug trial or device in the last 1month. 4. To have a history or presence of clinically significant medical, psychiatric, or emotional condition. The study will be conducted at the University of Buea in Cameroon, and the University of Rwanda. All students and staff members of the University will be invited to participate. In the University of Buea, there are about 12,000 students and 973 staff members (500 teachers and 473 administrative /supporting staff. The University of Rwanda (UR), has about 30,445 students and 2,266 staff members (1450 teachers and 816 administrative /supporting) Composition of The study treatments (Artemisia Afra) and control (placebo) will be prepared in the various study and formulations as follows: control Artemisia afra available as infusions containing 5g of Artemisia per liter, will be prepared by adding treatments 5 g dried leaves and twigs of A. afra (in a tea sachet / tea bag) to 1 liter of boiling water, infused for 10 min, and filtered through a sterilized 1 mm mesh. Artemisia afra available as infusions containing 5g of Artemisia in per 500ml, will be prepared by adding 5 g dried leaves and twigs of A. afra (in a tea sachet / tea bag) to 500ml of boiling water, infused for 10 min, and filtered through a sterilized 1 mm mesh. Flavored Artemisia afra available as infusions containing 5g of flavored Artemisia per liter, will be prepared by adding 5 g of flavored dried leaves and twigs of A. afra (in a tea sachet / tea bag) to 1 liter of boiling water, infused for 10 min, and filtered through a sterilized 1 mm mesh. Flavored Artemisia afra available as infusions containing 5g of flavored Artemisia per 500ml, will be prepared by adding 5 g of flavored dried leaves and twigs of A. afra (in a tea sachet / tea bag) to 500mls of boiling water, infused for 10 min, and filtered through a sterilized 1 mm mesh. Flavored placebo available as infusions containing flavored inactive substance per liter, will be prepared by adding flavored inactive substance (in a tea sachet / tea bag) to 1 liter of boiling water, infused for 10 min, and filtered through a sterilized 1 mm mesh. Regular tea placebo will be any tea of choice routinely taken by the selected participants. After preparation, the following doses will be obtained for consumption by participants with

respect to study arm.

	Drug components	Non-flavored	Flavored
	Artemesia afra 5g	Artemesia 5g/ 1liter	Artemesia 5g/ 1liter,
		1.25g/250 ml dose	1.25g/250 ml dose
	Artemesia afra 5g	Artemesia 5g/ 500ml,	Artemesia 5g/ 500ml,
		2.5g/250 ml dose	2.5g/250 ml dose
	Placebo	Regular tea placebo	Flavored placebo
			250ml dose
Study	This study will use the adap	ted Zelen design which has two st	eps in the consent process. At step
		ifter informed consent is obtained ill be done and sociodemographic rior medications information and Il be collected from each participanting malaria rapid diagnostic test kill be repeated for negative samples mples will be further analyzed with quantification and specific stage. Participants who fulfil the inclusion 2: 2:2:2: 1:1 ratio for the 6 treatment in and a second consent will be assed on the allocation arm. The 6 trial arms versus favored placebone participants who will decline to	
	Follow up visits. During 4 consecutive weeks, once a week on Day 7, 14, During the 4 weeks, participations.	28 and 35, in order to assess gam	etocyte elimination rate with teas

• Proportion of people with decreased gametocyte load after treatment with *Artemisia afra* tea on Day 35 from baseline.

Secondary endpoints

- Level of decrease in gametocyte load (rt-PCR Ct) in the different treatment arms at D7, D14, D28, and D35 from baseline (activity level and optimal dosage schedule).
- Level of decrease in gametocyte load the various treatment arms (rt-PCR Ct) by gender, age, and trial entry parasite load, at D7, D14, D28, and D35 from baseline.
- Proportion of people in the various treatment arms who respect and complete the prescribed treatment dosages (accepted dosage schedule and drug formulation).

	Variability and Proportion of persons on the various treatment arms who develop clinical			
	symptoms, ASEs, or AES at D7, D14, D28, and D35 from baseline (No severe adverse side			
	effects are expected).			
	Proportion of persons with baseline discordant test results (False positive or false negative)			
	between mRDT, rt-PCR, and direct blood smear observation.			
	Exploratory endpoints.			
	Variability in level of decease in gametocyte load (rt-PCR Ct) in the various treatment arms			
	at D7, D14, D28, and D35 from baseline.			
	Variability in level of decease in gametocyte load (rt-PCR Ct) in the various treatment arms			
	by gender, age, and trial entry parasite load, at D7, D14, D28, and D35 from baseline.			

1. INTRODUCTION, BACKGROUND AND RATIONALE

Malaria is a preventable disease caused by the Plasmodium parasite and transmitted by female Anopheles mosquitoes (1). Plasmodium parasites exhibit a complex life cycle that includes three stages in the human host and one sexual development stage in the mosquito vector (2). During replication in the human blood stream, some of the merozoites differentiate into sexual forms of the parasite, called *gametocytes*, and pass into the blood stream. When a mosquito bites an infected human during a blood meal, it ingests the gametocytes, and these undergo sexual development in the mosquito vector to continue the plasmodium cycle (Figure 1) (2). Successful elimination of malaria can only be achieved through optimal vector control (e.g. genetically modifying female mosquitoes) and complete depletion of the infectious reservoir in humans (3). However, symptomatic malaria cases are only a small proportion of all infectious reservoirs in malaria endemic settings, and most (>95%) of the human infectious reservoirs are asymptomatic parasite carriers (4,5). Accurate identification and treatment of asymptomatic infectious human reservoirs is therefore a critical step to an effective malaria elimination process.

[figure not shown]

Figure 1. Plasmodium life cycle (Source: Maier et al 2019)

2.2 Literature review

Malaria parasite transmission is highly heterogeneous across the various zones in Africa. Out of 5 parasite species that cause malaria in humans, 2 of these species – P. falciparum and P. vivax – pose the greatest threat, P. falciparum accounted for over 99% of the cases in the WHO African Region in 2018 (1) Significant and continual efforts/innovation in the fight against malaria, has led to a substantial decline in global malaria morbidity and mortality, but malaria elimination in most malaria-endemic settings remains a core public health concern. So far, there are no vaccine disrupting the disease transmission (2). The most advanced vaccine approved for pilot use is Mosquirix, developed by GSK, which has an efficacy of 30-53% and 56% in phase II and III trials, respectively, quite below the 75% target expected by WHO (6). Recently, initial findings from a new vaccine trial R21/Matrix-M under development by Oxford, showed up to 77% efficacy on Burkinabe children (7). Current control measures in place encompass the use of WHO recommended strategies that include vector control (insecticide treated nets (ITNs) and indoor residual spraying (IRS)), early diagnosis and prompt treatment of symptomatic cases, as well as chemoprophylaxis for high-risk population groups as children under 5, pregnant women and naïve visitors (8). These measures have reduced malaria burdens globally in recent years, and raised hopes for malaria elimination/eradication in the near future (9–11). However, these hopes are severely threatened by the emergence of resistances for both insecticide and antimalarial drugs like Artemisinin-based combination therapies (ACTs) that are the first line WHO recommended malaria treatment (12-14). Furthermore, the current malaria control measures focus on the mosquito stage and the two asexual human stages, but do not target the gametocyte stage which allows the parasite transmission from humans to the mosquito vector for the disease perpetuation.

Gametocytes are insensitive to most conventional antimalarial drugs and often persist in the blood

stream after successful antimalarial therapy, thereby ensuring continued malaria transmission over several months after the clearance of asexual parasites (16,17). Primaquine and the fast-acting but short-lived artemisinin-based drugs are the only antimalarials that have exhibited gametocytocidal activities (17), but primaquine is toxic in persons with glucose 6 phosphate dehydrogenase deficiency, limiting its general use in most countries (19, 20). A novel antimalarial compound called Cipargamin (KAE609) compound which is said to exert gametocidal activity with transmission blocking potential, is still undergoing phase 2 clinical trial to assess its safety and efficacy (20).

Furthermore, while the mosquito vector may harbor the sexual forms of the parasite through its entire adulthood of 1-2 months, the human host can remain asymptomatic for the asexual parasite stages for up to 13 years, during which transmissible gametocyte forms are continually released into the blood stream (21). This results in the widespread occurrence of asymptomatic plasmodium reservoirs, who often do not seek antimalarial treatment, due to the absence of clinical illness.

Studies reveal that asymptomatic reservoirs can be eliminated in mass treatment programs (23,24). Various mass treatment strategies such as Mass drug administration (MDA) have been proposed and proven to rapidly reduce malaria burdens particularly in regions with seasonal malaria transmission in Africa and in China, (23–26). Unfortunately, the MDA strategy has not been successful with the ACTs, as drug resistance and potentiation of gametocyte transmission has rather been observed upon ACT administration (28, 29). On the other hand, surveys have reported the protective effect of Artemisia teas against malaria in communities that use its herbal teas for malaria prevention (29). Meanwhile other studies have demonstrated that *Artemisia annua* and *Artemisia afra* infusions or powdered leaves reduces parasitemia and kills transmissible gametocyte forms, with characteristic chemoprotective potentials (30–33).

Rationale

The WHO African Region carries a disproportionately high share (94%) of the global malaria burden (1). Repeated calls from WHO have advocated for mobilization and expanded actions towards malaria elimination in the continent. As a result, there has been extraordinary and optimistic scale-up of WHO recommended malaria control interventions in most African countries over the last decades. Despite the recent progress on reducing malaria morbidity and mortality in response to this, empirical and theoretical evidence show that current control interventions alone will not be sufficient to eliminate malaria from many endemic regions in sub-Saharan Africa. Thereby suggesting that current interventions be supplemented by additional strategies, for effective elimination in most sub-Saharan Africa countries (5).

An emergence of resistances for both insecticide and antimalarial drugs like ACTs has been reported in several African countries. In addition, these strategies are restricted to indoor controls and populations

remain exposed to Plasmodium transmission during their outdoor activities. These strategies also fail to target asymptomatic Plasmodium carriers who constitutes, most of the infected people in endemic regions (4, 5) and perpetuate the disease transmission over time. Hence, the need to accurately identify and treat asymptomatic infectious human reservoirs.

Reports of investigations that *Artemisia afra* tea infusions can effectively treat malaria in endemic communities, with gametocidal effects and no reported toxicity (29–31), are promising and suggest its probable usefulness in the elimination of plasmodium reservoirs in endemic settings. However, no clinical trials have not been conducted to ascertain the activity level and optimal dosage of *Artemisia afra* tea in the treatment of asymptomatic reservoirs.

2. HYPOTHESIS, OBJECTIVES AND ENDPOINTS

Hypothesis: An optimal dosage of artemisia afra tea infusions is effective, safe, and well tolerated in eliminating plasmodium reservoirs.

Research Objectives

2.3.1 Primary objective

To find the activity level and accepted optimal dose concentration, dose frequency, length of treatment, and formulation (flavor) of *A.afra* in treating Plasmodium reservoirs.

2.3.2 Secondary objectives

- 1. To assess participants response (treatment efficacy) to varying dose concentrations, dose frequency, length of treatment, and formulation of *Artemisia afra* treatment.
- 2. To identify the most acceptable dose concentration, dose frequency, length of treatment, and formulation (flavor) of Artemisia treatment.
- 3. To assess the safety (ASE) of *Artemisia afra* treatment in participants by dose concentration, dose frequency, length of treatment, and formulation. As a commonly used tea, no toxicity is expected.
- 4. To assess variability of plasmodium test predictive values between mRDT, rtPCR, and direct blood smear observation in asymptomatic persons.

Treatment outcomes

Major outcome

• Decrease in parasite load over time.

Secondary outcomes

- Decrease in gametocyte load in carriers with Artemisia afra tea by dose concentration, dose frequency, length of treatment, and formulation.
- Acceptability (adherence and completion) of *Artemisia afra* treatment by dose concentration, dose frequency, length of treatment, and formulation (flavor).

- Safety (SAEs) of *Artemisia afra* treatment in participants by dose concentration, dose frequency length of treatment, and treatment formulation.
- Absolute increase in Cycle threshold (Ct >20).
- Likelihood and variability in the rate of reservoir elimination with treatment, compliance/ acceptability, and occurrence of side effects /adverse events in different treatment arms.

Treatment endpoints

Primary endpoints

• Proportion of people with decreased gametocyte load after treatment with *Artemisia afra* tea on Day 35 from baseline.

Secondary endpoints

- Level of decrease in gametocyte load (rt-PCR Ct) in the different treatment arms at D7, D14, D28, and D35 from baseline (activity level and optimal dosage schedule).
- Level of decrease in gametocyte load the various treatment arms (rt-PCR Ct) by gender, age, and trial entry parasite load, at D7, D14, D28, and D35 from baseline.
- Absolute increase in Cycle threshold (Ct >20) in various treatment arms at D7, D14, D28, and D35 from baseline.
- Proportion of people in the various treatment arms who respect and complete the prescribed treatment dosages (accepted dosage schedule and drug formulation).
- Proportion of persons on the various arms of treatment who develop clinical symptoms at D7, D14,
 D28, and D35 from baseline.
- Proportion of people on the various arms of treatment who develop ASEs or AEs at D7, D14, D28, and D35 from baseline (No severe adverse side effects are expected).
- Proportion of persons on the various arms of treatment who withdraw from study due to severe ASEs or AEs at D7, D14, D28, and D35 from baseline.
- Proportion of persons on the various arms of treatment who withdraw from study for reasons other than severe AEs at D7, D14, D28, and D35 from baseline.
- Proportion of persons with baseline discordant test results (False positive or false negative) between mRDT, rt PCR, and direct blood smear observation?

Exploratory endpoints

- Variability in level of decease in gametocyte load (rt-PCR Ct) in the various treatment arms at D7, D14, D28, and D35 from baseline.
- Variability in level of decease in gametocyte load (rt-PCR Ct) in the various treatment arms by gender, age, and trial entry parasite load, at D7, D14, D28, and D35 from baseline.
- Variability in attainment of absolute increase in Cycle threshold (Ct >20) in the various treatment arms at D7, D14, D28, and D35 from baseline.

- Variability in the proportion of participant who respect and complete prescribed treatment dosages (acceptability) in the various treatment arms.
- Variability in the proportion of participants who develop clinical symptoms in the various treatment arms at D7, D14, D28, and D35 from baseline.
- Variability in the proportion of participants who develop Severe ASEs in the various treatment arms at D7, D14, D28, and D35 from baseline (not expected).
- Variability in proportion of participants who withdraw from the study due to severe ASEs, in the various treatment arms, at D7, D14, D28, and D35 from baseline.
- Variability in proportion of participants who withdraw from the study for reasons other than severe AEs, in the various arms of treatment at D7, D14, D28, and D35 from baseline.

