Randomization: Prior to treatment, eligible participants will be randomly assigned into the 8 study arms. The randomization method will be a permuted block randomization, with a block size of either 14 or 28 at random, and with a two-to-one allocation ratio for each active arm against two different control arms (2:2:2:2:2:1:1).

Blinding: The participants in the intervention arms will be aware of their assignment to an intervention group but unaware of the treatment assigned to them. The site staff (investigators or observers) will be

aware of assignments to one control arm (regular tea group), but unaware of assignments in the other treatment arms.

Visits/assessment schedules: A total of five study visits will be effected, being one baseline visit on Day 0, and four follow-up visits on Day 7, 14, 28 and 35, from baseline. During the baseline visit plasmodium tests targeting specific parts of the gametocyte genes will be done to determine the participants' initial (baseline) parasite load, and during subsequent visits, follow up control tests (rtPCR and blood smear) will be done, and the gametocyte load recorded, alongside assessments for clinical symptoms and adverse sides effects (if any).

Endpoints The efficacy of each of the treatment dosage schedule will be evaluated on day 7,14,28 and 35 from baseline, based on response to treatment or reservoir elimination rate. Response to treatment will be indicated by an absolute increase in Cycle threshold (Ct >20), or a negative rt-PCR tests results (Ct >40). If the patient misses the follow-up visit, compliance will be noted in the completion worksheet (filled out at end of study) and the parasite load and adverse side effects noted during the last visit considered. No severe side adverse effects are expected from the treatment but since toxicity is always a concern in clinical trials involving humans, participants will be observed for any severe ASEs and withdrawal noted throughout the study duration.

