5.7 Laboratory tests

Before randomization during the baseline visit (D0), blood samples will be collected from each participant and examined for the presence of parasites (Gametocytes) using Malaria rapid diagnostic test kit (BIOCREDIT Malaria Ag P.f/Pan RDT). RDT positive samples will be re-examined with qPCR (quantitative polymerase chain reaction) and direct microscopy for confirmation. The qCPR will be repeated for negative samples and participants excluded if still negative. All qPCR positive samples will be further analyzed with rt PCR (real time polymerase chain reaction), for parasite quantification and specific stage identification, targeting specific parts of the gametocyte genes.

- a. *BIOCREDIT Malaria Ag P.f/Pan RDT*: This is a three-band RDT that detects HRP2 and pan-pLDH antigens which will detect the presence of P. falciparum (HRP2) and of another specie (pan-pLDH). Results will be interpreted as Negative (band absent) Mildly positive (faint band appearance) strongly positive (conspicuous band appearance).
- b. *Direct microscopy*: Direct Microscopic identification of parasites will be performed using thin and thick blood films stained with Giemsa and quantified as number of parasites per milliliter of blood.
- c. *rtPCR*): The parasite load will be measured based on the number of rtPCR cycle thresholds (Ct) (which is an inverse proportion of the parasite load) and classified as absolute increase in Cycle threshold (Ct >20), or negative rt-PCR tests results (Ct >40).
- d. *Blood sample schedule*: Five blood samples (approximately 1mL each) will be collected at Visit 1 (Day 0), Visit 2 (Day 7), Visit 3 (Day 14), Visit 4 (day 28), and visit 5 (day 35). After conducting the 3 or 4 tests at visit 1, only the rtPCR test and blood smear microscopy will be done during subsequent evaluations.

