8. STATISTICAL CONSIDERATIONS AND ANALYSIS PLAN

8.1 Sample size calculations

As a pilot study, we will recruit 8 asymptomatic plasmodium carriers per study-arm in the 6 trial arms and 4 participants per arm in the 2 control (placebo) arms. Therefore 56 positive participants will be enrolled per site, making 112 participants in the whole study. To reach the required number of 56 gametocyte carriers, 635 persons will be RDT tested in Buea (south west region) where the expected positive RDT was 9.8% in Demographic health survey (DHS) 2018 (34) and drop-out rate was set at 10%. In Huye (South region) where the expected positive RDT was 6.9% in Malaria indicator survey (MIS) 2017 (35) and drop-out rate was set at 10%, 432 persons will be RDT tested to reach the required number of 56 gametocyte carriers.

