8.3 Analysis Plan

➤ Data management and analysis: All data will be entered into an Excel spreadsheet and then analyzed STATA 17 software packages. Descriptive statistics will be used to redistribute the treatment outcomes in the various treatment arms according to the evaluation times.

Quantitative variables will be summarized using means and medians followed by their standard deviations (SD) and Interquartile range (IQR) respectively, while qualitative variables will be summarized as percentages. Groups will be compared using a linear mixed model and trends over time will be compared using F-tests at 95% CI and statistical significance set at P < 0.05.

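### The primary endpoint keeps only the sign of a continuous Ct change; if most participants on active tea improve, it discards more than half the information for comparing regimens

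*Protocol*

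**What the plan says.** Section 2.3.1 gives the primary objective as "To find the activity level and accepted optimal dose concentration, dose frequency, length of treatment, and formulation (flavor) of" *A. afra*. This is a comparison among six active arms.

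Under Treatment endpoints in section 2.3.2, the single primary endpoint is "Proportion of people with decreased gametocyte load after treatment with" the tea on Day 35 from baseline. The synopsis has the same wording. Neither place says how large a decrease must be.

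The measurement itself is continuous. Section 5.7 says "The parasite load will be measured based on the number of rtPCR cycle thresholds (Ct"), with Ct inversely related to load. The first secondary endpoint is "Level of decrease in gametocyte load (rt-PCR Ct) in the different treatment arms at D7, D14, D28, and D35 from baseline". Its label, "from baseline (activity level and optimal dosage schedule"), repeats terms of the primary objective.

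Section 3 has another definition: "Response to treatment will be indicated by an absolute increase in Cycle threshold (Ct >20), or a negative rt-PCR tests results (Ct >40"). The primary endpoint does not use it.

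For analysis, section 8.3 states: "Groups will be compared using a linear mixed model and trends over time will be compared using F-tests at 95% CI". On size, section 8.1 states: "we will recruit 8 asymptomatic plasmodium carriers per study-arm in the 6 trial arms", with 4 in each of two control arms, at each of two sites. The synopsis says that no formal sample size calculation was done.

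**The concern.** Choosing among regimens means comparing how much each one lowers the load. An endpoint that records only whether the load fell gives the same score to a small fall and to near-clearance. If the tea works as the protocol hypothesises, many participants in every active arm will show some decrease. The proportions then crowd towards 100% and differ little between regimens, even where the sizes of the falls differ clearly.

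With 16 participants per active arm there is little information to spare. At stake is whether the trial's primary result can speak to its primary objective, when a measure already collected at every visit could do so better.

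**Working it through.** **Group sizes.** Per site: 6 × 8 + 2 × 4 = 56. Two sites: 112. Both match section 8.1. Over both sites this gives 16 per active arm and 8 per control arm, so 32 per schedule if the flavoured and unflavoured arms are pooled, and 16 controls if both control arms are pooled. The protocol states no power, so there is no power figure to reproduce.

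**Assumptions (not in the protocol).** Change in Ct is normal with a common SD. Effects μ are in SD units. A decrease in load means a change in Ct above 0, so the proportion decreased is p = Φ(μ). Tests are two-sided at 5%, with no dropout and no multiplicity adjustment. The protocol names no test for the proportion, so chi-square (uncorrected) and Fisher are both shown.

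**Information kept by the sign.** Relative efficiency is φ(z_p)² / [p(1 − p)]:

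- p = 50%: 0.399² / 0.25 = 0.64
- p = 70%: 0.348² / 0.21 = 0.58
- p = 80%: 0.280² / 0.16 = 0.49
- p = 90%: 0.1755² / 0.09 = 0.34
- p = 95%: 0.1031² / 0.0475 = 0.22

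It falls to one half at p = 79%.

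**Power between two single arms, 16 v 16, true difference 1 SD.** For the t-test the noncentrality is 1 / √(1/16 + 1/16) = 2.83 on 30 degrees of freedom, giving 78%. Yes/no powers are by exact enumeration:

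| Decreased | Full scale (t) | Chi-square | Fisher |
|---|---|---|---|
| 84% v 50% | 78% | 58% | 39% |
| 93% v 69% | 78% | 44% | 27% |
| 98% v 84% | 78% | 18% | 7% |
| 99% v 93% | 78% | 2% | 0.3% |

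**Against control.** For one schedule pooled over flavour v both controls pooled (32 v 16, controls at 50% decreased):

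- 0.5 SD: 36% (t) v 27% (chi-square), a loss of 9 points
- 0.75 SD: 67% v 51%, a loss of 16 points

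**Picking the best of six arms** (16 per arm, one arm 1 SD better, 20,000 simulated trials, ties broken at random). The mean change picks correctly in 99% of runs throughout. The proportion decreased picks correctly in 94%, 87%, 71% and 42% of runs when the other five arms are at 50%, 69%, 84% and 93% decreased.

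**Effect of the Ct ceiling.** Section 5.7 treats Ct above 40 as negative, so the full scale is itself capped. Further assumptions are SD of change 4 cycles, baseline SD 3, and mean baseline Ct from 28 to 35. With 32 v 32 and follow-up Ct capped at 40, the baseline-adjusted comparison has about 84% to 97% power for effects of 2.0 v 1.0 SD, against about 53% for the sign (chi-square). For 2.5 v 1.5 SD it has about 71% to 96%, against about 14%.

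**The case against.** The strongest case on the other side has four parts.

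- **Saturation is an assumption about the results.** A reader might infer that the endpoint will saturate in the active arms and lose most of its power. The protocol gives no response rate, SD or effect size, so it does not support that as a fact. At 84% v 50% decreased, about a quarter (chi-square) to a half (Fisher) of the power is lost. Against control the loss is smaller again. This part stands, and the point is therefore conditional.
- **The comparison of regimens is already planned.** A reader might infer that the primary objective goes unanswered. It does not. The level of decrease by arm at four visits is a prespecified secondary endpoint, the major outcome is a decrease in load over time, and section 8.3 names a mixed model suited to both. In a pilot without a stated success rule, the primary label also carries less weight. This stands too, but the endpoint that best fits the primary objective is still the one ranked second.
- **Ct has a ceiling.** If the tea clears parasites, change in Ct is censored at 40. Without baseline adjustment, power for 2.5 v 1.5 SD (32 v 32) falls to 36% at a mean baseline Ct of 35. The advantage narrows but remains, and adjusting for baseline recovers much of it. Any fix needs a rule for negative results.
- **The sample is small on either scale.** For 1.5 v 1.0 SD with 16 v 16, the full scale has only 28% power (chi-square 9%). The swap improves the comparison but does not make it reliable for modest differences.

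**Conclusion.** The point holds in conditional form. As written, any decrease counts as success, so the primary endpoint is the sign of a continuous change, while the endpoint labelled with the objective's own terms is secondary.

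How much is lost depends on how many participants improve, which the documents do not say. Under normal Ct change, about 36% of the information goes when 50% improve, and more than half goes from about 79% upwards. The upper range is plausible if the hypothesis in section 2 is right. For single arms differing by 1 SD, that means 78% power against 58% or 39% at the favourable end, and 18% or 7% at 98% v 84%. Against control it costs about 9 to 16 points by chi-square for effects of 0.5 to 0.75 SD.

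No stated power is contradicted, because none is stated. This is an inexpensive improvement worth making; it does not show that the trial cannot compare its regimens.

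**What to change.** In the synopsis and in section 2.3.2, identically:

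1. Make the primary endpoint the change in gametocyte rt-PCR Ct from baseline to Day 35. Ct is already on a log2-type scale, so no further log should be taken.
2. Analyse it with the linear mixed model of section 8.3, with baseline Ct as a covariate.
3. State in advance how negative results (Ct above 40) enter: either set to 40 or treated as censored.
4. Keep the proportion with decreased load as a secondary descriptive summary.

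The cost is wording only: an existing primary and an existing secondary endpoint change places, with no new samples, assays or participants. There are two downsides. A mean Ct change is harder to communicate than a percentage, which is why the percentage stays in the report. The gain also shrinks if most participants become PCR negative.
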